6.3.4. Tertiary/Exploratory Analyses

ACR20, Hybrid ACR, each ACR component, DAS-hsCRP, and morning joint stiffness duration are exploratory endpoints in Part A. Data will be summarized by treatment and each postbaseline visit.

6.3.4.1. Morning Joint Stiffness Duration

Subjects will be asked to assess their duration of morning joint stiffness on the day prior to the visit. Responses will be recorded in minutes. Durations longer than 12 hours (720 minutes) will be truncated to 720 minutes for analysis. Duration of pre-visit morning joint stiffness will be recorded at baseline and all postbaseline visits. Summary statistics of the actual duration and change from baseline will be performed by treatment and each postbaseline visit.

The comparison between each LY3337641 dose and placebo in duration of morning joint stiffness change from baseline through Week 12 in Part B will be analyzed using a Wilcoxon rank-sum test controlled by biologic DMARD experience (yes/no) and baseline DAS28-hsCRP categories ($\leq 5.1 / > 5.1$). The median difference of the change from baseline score and its 95% CI will be estimated by the Hodges-Lehmann method. The mLOCF approach will be used to impute missing data.

6.3.4.2. Patient's Assessment of Sexual Function (VAS)

Subjects will be asked to assess the extent of the effect that RA has had on their sexual activity over the past week by marking a vertical tick on a 100-mm horizontal VAS, on which the left end (0) represents "no effect on my sexual activity" and the right end (100) represents "completely stopped my sexual activity" in Part B.

The sexual activity score (VAS) and the change from baseline will be summarized by treatment and each postbaseline visit. An MMRM model will be used to analyze change from baseline for schedule postbaseline time points. Baseline, treatment, weeks of treatment (categorical), the interaction of treatment and weeks region (Japan versus non-Japan), biologic DMARD experience (yes/no), and baseline DAS28-hsCRP are fixed effects; subjects and error are random effects.

6.3.4.3. SF-36

The SF-36v2 Acute measure version 2 (SF-36) is a subjective, generic, health-related quality of life instrument that is patient-reported and consists of 36 questions covering 8 health domains: physical functioning, bodily pain, role limitations due to physical problems, role limitations due to emotional problems, general health perceptions, mental health, social function, and vitality. Each domain is scored by summing the individual items and transforming the scores into a 0 to 100 scale with higher scores indicating better health status or functioning. In addition, 2 summary scores, the PCS (physical component score) and the MCS (mental component score), will be evaluated based on the 8 SF-36 Acute domains (Brazier et al. 1992; Ware and Sherbourne 1992). The SF-36 is collected for Part B only.

Summaries of domain scores and summary scores will be provided by visit and change from baseline to postbaseline visits. The change from baseline in domain scores, the summary scores to each scheduled postbaseline time point in Dosing Period will be analyzed by the MMRM model will be used to analyze change from baseline to each scheduled postbaseline time point. Baseline, treatment, weeks of treatment (categorical), the interaction of treatment and weeks, region (Japan versus non-Japan), biologic DMARD experience (yes/no), and baseline DAS28-hsCRP are fixed effects; subjects and error are random effects.

The Minimum Clinically Important Difference (MCID) of MCS and PCS is defined as ≥ 2.50 increase in the change from baseline value (Kosinski et al. 2000; Strand and Singh 2010). Number and percentage of subjects with MCID in MCS and PCS will be summarized by treatment and each postbaseline visit. Each LY3337641 dose group will be compared to placebo using a Cochran-Mantel-Haenszel test, adjusting for biologic DMARD experience (yes/no), and baseline DAS28-hsCRP category ($\leq 5.1 / > 5.1$).

6.3.4.4. Functional Assessment of Chronic Illness Therapy -Fatigue Scores (FACIT-F)

The FACIT-F scale (Cella and Webster 1997) is a brief, 13-item, symptom-specific questionnaire that specifically assesses the self-reported severity of fatigue and its impact upon daily activities and functioning. The FACIT-F uses 0 (“not at all”) to 4 (“very much”) numeric rating scales to assess fatigue and its impact in the past 7 days. Scores range from 0 to 52 with higher scores indicating less fatigue.

The Minimum Clinically Important Difference (MCID) FACIT-F score is defined as ≥ 3.56 change from baseline value of the Fatigue Subscale Score. The summary and analysis of the FACIT-F score will include the number of patients achieving the MCID at each postbaseline visit. The proportion of patients achieving the FACIT-F score MCID will also be analyzed using a logistic regression model with treatment, region, and baseline joint erosion status (yes/no) as fixed effects.

The change from baseline in FACIT-Fatigue to each scheduled postbaseline time point in Part B will be analyzed by the MMRM model. Baseline, treatment, weeks of treatment (categorical), the interaction of treatment and weeks, region (Japan versus non-Japan), biologic DMARD experience (yes/no), and baseline DAS28-hsCRP are fixed effects; subjects and error are random effects. Each LY3337641 dose group will be compared to placebo using a Cochran-Mantel-Haenszel test, adjusting for biologic DMARD experience (yes/no), and baseline DAS28-hsCRP category ($\leq 5.1 / > 5.1$).

6.3.4.5. Biomarkers

BTK occupancy and Phosphorylated BTKi (pBTK) will be assessed at baseline and all postbaseline visits during the Dosing Period if validated assays are available; samples will be drawn only at sites that meet assay requirements. BTK occupancy will be calculated in 3 methods.

$$\text{Method 1 } \textit{Occupancy} = (BTK_{total} - BTK_{free}) / BTK_{total}$$

Method 2

$$\textit{Occupancy} \approx \frac{BTK_{total} - \min(\beta * BTK_{free}, BTK_{total})}{BTK_{total}} * 100$$

β : regression coefficient from the linear regression without intercept for BTK_{total} against BTK_{free} using all placebo data and baseline data from LY groups

Method 3

$$\textit{Occupancy} \approx BTK_{free} cfb = \frac{\frac{BTK_{free, BL} - \min(\frac{BTK_{free, BL}}{TotProt_{BL}}, \frac{BTK_{free}}{TotProt})}{BTK_{free, BL}}}{\frac{BTK_{free, BL}}{TotProt_{BL}}} * 100$$

cfb : change from baseline; BL : baseline

The analytes of interest of pBTKi are %pPLCy2+ (CD19+), %pPLCy2+ (CD14+), MEFLpPLCy2 (CD19+), MEFLpPLCy2 (CD14+), MEFL pBTK/pITK (CD19+), MEFL pBTK/pITK (CD14+), %pBTK/pITK+ (CD3+/CD4+), MEFL pBTK/pITK (CD3+/CD4+), %pBTK/pITK+ (CD3+/CD8+), and MEFL pBTK/pITK (CD3+/CD8+). All analytes of this panel are in [Appendix 2](#).

Flow cytometry will be assessed at baseline and all postbaseline visits during the Dosing Period in Part B. All analytes of flow cytometry are listed in [Appendix 3](#). The analytes of interest of flow cytometry are:

- TBNK Panel (absolute value and the percentage):
CD3 Cyto-Chex BCT-CL, CD8 Cyto-Chex BCT-CL, CD4 Cyto-Chex BCT-CL, CD16+56 Cyto-Chex BCT-CL, and CD19 Cyto-Chex BCT-CL.
- NK Panel (absolute value and the percentage):
CD69 NK cells, CD69 T cells, CD69 CD4 T cells, and CD69 CD8 T cells.

BTK occupancy, interested analytes of pBTK, and interested analytes in flow cytometry will be summarized over time by treatment. Data will be further explored using Spotfire.

6.3.4.6. Autoantibodies and Immunoglobulins

Rheumatoid factor (RF), anti-cyclic citrullinated peptide antibodies (ACPA), total immunoglobulins (Ig) and Ig classes (IgG, IgA, and IgM) lab data will be collected at screening in Part A. These will be collected at screening and Week 12 or end of treatment in Part B. The actual measures and change from screening to Week 12 or end of treatment in Part B will be summarized by treatment. In addition, shift tables of screening seropositivity to Week 12 or end of treatment seropositivity will be produced for tests with normal reference ranges.

6.3.4.7. Dose-Response Relationship

6.3.4.7.1. Trend Test

The trend test will be used for exploring the drug-related improvement based on the primary measure (that is, ACR20 at Week 12) and additional efficacy measures (for example, ACR50, ACRN, Hybrid ACR, and DAS28-hsCRP at Week 12) under the assumption of monotonic treatment response. This test will include 4 doses (30-mg, 10-mg, 5-mg LY3337641 and placebo). The assertion of trend implies that the efficacy measure improves with increasing doses.

The null hypothesis is $\{\mu_{\text{placebo}} = \mu_{\text{LY 5 mg}} = \mu_{\text{LY 10 mg}} = \mu_{\text{LY30 mg}}\}$.

The alternative hypothesis is $\{\mu_{\text{placebo}} \leq \mu_{\text{LY 5 mg}} \leq \mu_{\text{LY 10 mg}} \leq \mu_{\text{LY 30 mg}}, \text{ with at least 1 strict inequality}\}$.

6.3.4.7.2. Dose-Response Curve Characterization

The dose-response curve will be characterized using a nonlinear dose response E_{max} model including 4 doses (3 doses of LY3337641 and placebo). Given the estimated PD effect of doses

from the Phase 1 were not linear, a nonlinear model may provide an adequate approximation compared to linear assumption. Estimates of the nonlinear model parameters, LSM means of the efficacy variables by treatment, along with the 95% CIs will be reported.

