4.4. Justification for Dose

The LY3337641 dosage range of 5 to 30 mg qd administered orally is based on nonclinical toxicology data, clinical safety data from the Phase 1 study, as well as the effective BTK occupancies projected on the basis of both the Phase 1 clinical data and the nonclinical results. The maximum dose of 30 mg qd provides >1-fold exposure multiple (margin of safety) based on area under the curve (AUC) in 2 species (rat and monkey) at the NOAEL in the 13-week nonclinical toxicology studies (see Section 5.2.1 of the Investigator's Brochure [IB]). This dose is also below the highest dosage tested in the Phase 1 study (40 mg qd) at which there were no

skin rashes or significant TEAEs (that is, TEAEs leading to discontinuation or deemed significant by the investigator).

In a rat collagen-induced arthritis model, BTK occupancy of approximately 80% was sufficient to achieve efficacy. On the basis of Phase 1 BTK occupancy data in humans, 30 mg qd is expected to achieve BTK occupancy of approximately 90%. The 5- and 10-mg qd dosages are projected to achieve BTK occupancy of approximately 70% and 80%, respectively. Thus, this study will test dosages that were well tolerated in the Phase 1 study and are projected to achieve BTK occupancies that are expected to be efficacious.

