5.2. Determination of Sample Size

Approximately 32 at least mildly active RA subjects will be enrolled and randomly assigned in a 1:1:1:1 ratio to 1 of the 3 doses of LY3337641 (5, 10, or 30 mg) or placebo in Part A. This sample size is customary for evaluating safety and PK and/or PD parameters, and is not powered on the basis of statistical hypothesis testing.

Approximately 244 moderately to severely active RA subjects will be enrolled and randomly assigned in a 1:1:1:1 ratio to 1 of the 3 doses of LY3337641 (5, 10, or 30 mg) or placebo in Part B. All subjects who discontinue the treatment early (before Week 12) will be considered as failing the primary endpoint in Part B. The sample size of 61 subjects per arm will provide at least 80% power at the 2-sided .05 significance level to detect a difference of 25% in the primary endpoint (ACR20 response rate at Week 12) between each LY3337641 dose and placebo, assuming a 30% placebo response rate.

If the assessment committee determines that a dose adjustment is needed, the total study sample size may be adjusted.

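### The Emax ED50 that the SAP promises with a 95% CI would be too imprecise to use for ACR20, and the trend-test alternative points the wrong way for DAS28-hsCRP

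*SAP*

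**What the plan says.** SAP 6.3.4.7.2 characterises dose-response with a nonlinear Emax model on four dose levels, placebo included. The promised output is: "Estimates of the nonlinear model parameters, LSM means of the efficacy variables by treatment, along with the 95% CIs will be reported". The section gives no link function, no bounds or prior, and no rule for non-convergence or a boundary estimate. SAP 4.2 and Protocol Table JPDA.2 name dose-response model parameters as the endpoint for this objective, at tertiary/exploratory level.

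The Part B size is fixed by the primary endpoint: "The sample size of 61 subjects per arm will provide at least 80% power" (SAP 5.2). The target there is a gain of 25 points in ACR20 over a placebo rate of 30%, tested two-sided at 0.05.

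Protocol 4.4 gives the projected BTK occupancy: "The 5- and 10-mg qd dosages are projected to achieve BTK occupancy of approximately 70% and 80%, respectively". It expects about 90% at 30 mg.

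SAP 6.3.4.7.1 applies a trend test to ACR20 and to further measures, DAS28-hsCRP among them. In words: "The assertion of trend implies that the efficacy measure improves with increasing doses". In symbols, the alternative is μ(placebo) ≤ μ(5 mg) ≤ μ(10 mg) ≤ μ(30 mg) with at least one strict inequality, in the same form for every measure. No test statistic, scores or contrast is named.

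**The concern.** An Emax curve has three parameters: placebo level, maximum effect and ED50. With four dose levels and a modest effect, a fit without bounds can drift towards a step (ED50 near zero) or a straight line (ED50 very large). The planned table would then show an ED50 at an arbitrary extreme, or an interval without a finite end, and the SAP does not say how to handle either. This parameter is the stated endpoint for the dose-response objective, and the study is meant to inform the design of later ones.

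The trend test raises a separate question. For DAS28-hsCRP lower is better: remission is a value below 2.6 (SAP 6.3.3.2), and change is postbaseline minus baseline (SAP 6.1.2). A mean that rises with dose therefore describes worsening, which contradicts the sentence just before the hypotheses.

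**Working it through.** **Plan's own figure.** Inputs from SAP 5.2: 61 per arm, 30% on placebo, 30% + 25% = 55% on active, two-sided 0.05.

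- Null SE = √(2 × 0.425 × 0.575 / 61) = 0.0895
- Alternative SE = √((0.30 × 0.70 + 0.55 × 0.45) / 61) = 0.0866
- Power = Φ((0.25 − 1.96 × 0.0895) / 0.0866) = Φ(0.86) = 80.5%

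The stated power is reproduced. The documents give no figure for the precision of the Emax fit.

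**Plausible ED50.** Assume that response is proportional to occupancy and that maximum occupancy is 100%; neither is in the documents. Then ED50 = dose × (1 − occupancy) / occupancy:

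- 5 mg: 5 × 0.3 / 0.7 = 2.14 mg
- 10 mg: 10 × 0.2 / 0.8 = 2.50 mg
- 30 mg: 30 × 0.1 / 0.9 = 3.33 mg

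**Approximate precision for ACR20** (Fisher information, 61 per arm, 30% rising to 55% at 30 mg). The 95% Wald interval is the estimate multiplied and divided by exp(1.96 × SE of log ED50).

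- ED50 2.14 mg: SE 1.84, factor about 37
- ED50 2.5 mg: SE 1.71, factor about 29, so roughly 2.5 / 29 = 0.09 mg to 2.5 × 29 = 72 mg
- ED50 3.33 mg: SE 1.54, factor about 20
- ED50 10 mg: SE 1.42, factor about 16

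A factor of 3 needs an SE of ln 3 / 1.96 = 0.56. That means 61 × (1.84 / 0.56)² ≈ 660 per arm at ED50 2.14 mg, and 61 × (1.54 / 0.56)² ≈ 460 at 3.33 mg.

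**Simulation for ACR20.** Binomial maximum likelihood with Emax on the logit scale, and a 95% profile interval on a grid from 0.01 to 1000 mg, 3,000 trials per row:

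| True ED50 (mg) | Estimate at grid edge | CI open below | CI open above | CI closed at both ends |
|---|---|---|---|---|
| 2.14 | 28% | 89% | 44% | 2.7% |
| 2.5 | 25% | 88% | 48% | 2.4% |
| 3.33 | 21% | 83% | 54% | 3.3% |
| 10 | 19% | 62% | 80% | 3.0% |

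A second set-up used least squares on arm proportions, a 30-mg effect of 15 or 25 points, ED50 2.1 or 3.3 mg, and 6,000 trials per scenario. The fitted ED50 was below 0.05 mg in 17-32% of trials and above 300 mg in 3-14%. The profile interval was open at one or both ends in 96-99.8%.

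**DAS28-hsCRP, Emax.** Assumed SD 1.2 and ED50 2.5 mg. With a difference from placebo at 30 mg of 0.6, 1.0 or 1.4, the interval is closed in 2%, 19% or 41% of trials, and the estimate is at the grid edge in 25%, 10% or 4%.

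**DAS28-hsCRP, direction of the trend test.** Assumed benefit 0.6 at 30 mg, SD 1.2, ED50 2.5 mg, one-sided 0.025, ordinal scores −1.5, −0.5, 0.5, 1.5.

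- Mean changes relative to placebo: 0, −0.433, −0.520, −0.600
- Contrast = 0.217 − 0.260 − 0.900 = −0.943
- SE = 1.2 × √(5 / 61) = 0.344, so z = −2.75
- Power in the written direction: Φ(−2.75 − 1.96), essentially 0%
- Power in the improving direction: Φ(2.75 − 1.96) = 78%

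**The case against.** A reader might infer from Protocol 4.4 that all three doses lie on a clinical plateau, so that ED50 cannot be estimated at all. The documents do not support that. The projection is of BTK occupancy, not of ACR20 or DAS28-hsCRP response. The protocol ties efficacy in a rat model to about 80% occupancy, and 5 mg is projected below that, so the clinical curve could still rise across the doses. Four dose levels do identify three parameters: 72-79% of the maximum-likelihood ACR20 simulations with ED50 2-3 mg give an interior estimate. Precision is also poor with ED50 at 10 mg, so arm size and effect size matter as well as dose placement.

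A reader might also infer that the trend test uses a contrast unsuited to a plateau. The SAP names no statistic, and its written alternative includes a flat plateau. Order-restricted tests that match this alternative have about 82-84% power for rates of 30/49/52/55%. The 60% that linear dose scores would give belongs to a choice the SAP did not make. The gap is one of specification.

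The direction error can fairly be called notation. The words state improvement, and SAP 6.1 makes tests two-sided at .05 unless otherwise stated; a two-sided contrast test would be unaffected. But an ordered alternative is one-sided in form, and the SAP does not say which reading governs.

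Finally, a wide interval in an exploratory analysis is an honest result, and treatment-group means with 95% CIs are already planned. Both points stand. They limit the consequence, but they do not tell the analyst what to report when ED50 is at an extreme or its interval is open.

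**Conclusion.** Two limited defects hold.

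1. For ACR20, the ED50 and its 95% CI would rarely be usable. About 20-45% of unbounded fits with ED50 at 2-3 mg run below 0.05 mg or above 300 mg, and about 97% or more of intervals are open on at least one side. At ED50 10 mg the picture is similar: 19% at the grid edge and 3.0% of intervals closed. The right description is lack of useful precision, not inestimability. Large DAS28-hsCRP effects would do better, though even a difference of 1.4 closes the interval in only 41% of trials.
2. The ordered alternative has the wrong direction for DAS28-hsCRP. The effect runs from none, if the test is two-sided, to a loss of essentially all power, if it is coded one-sided as written.

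The ED50 values of 2-3 mg rest on response proportional to occupancy with a 100% maximum. The DAS28-hsCRP figures rest on an assumed SD of 1.2 and differences of 0.6-1.4. None of these is in the documents. Both analyses are exploratory, and the primary logistic comparisons are untouched.

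**What to change.** - **SAP 6.3.4.7.2.** State the model scale and pre-specify bounds on ED50; 0.5-45 mg was tried and slightly lowered the error of the estimated 5- and 10-mg effects. Make model-based differences from placebo at each dose the main output, with bootstrap or profile intervals. Report ED50 only with a profile interval, and say when it is open or the estimate is at a bound.
- **SAP 6.3.4.7.1.** Reverse the inequality for DAS28-hsCRP, or define μ as mean improvement for every measure. State whether the test is one- or two-sided.
- **Optional.** Name a trend statistic that keeps power under a plateau, such as an order-restricted or multiple-contrast test.

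The cost is SAP wording and code, with no change to subjects, doses or sample size. The drawback is that the estimates will depend mildly on the chosen ED50 bounds, so these should be fixed before unblinding.

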6.3.4.8. Exposure-Response Relationship

The exposure-response relationship between LY3337641 exposure and key efficacy measures will be explored using graphical methods and/or a modeling approach. If a trend is noted in the graphical analyses, then further modeling using linear or E_{\max} models may be employed to describe the exposure-response relationship. Additional details for the exposure-response analyses will be provided in the Population PK/PD Analysis Plan.

6.4. Safety Analyses

All safety summaries and analyses will be based on the safety population as defined in Section 6.1.1. The safety population of the long-term extension (LTE) is defined in Section 6.5.5. Safety will be assessed by evaluating all reported AEs, AESIs, changes in vital signs, and changes in laboratory analytes.

Safety analyses will be conducted by randomized treatment for Part A and Part B separately. Follow-up Period will be summarized by the last used treatment in Part A or Part B. Subjects will be grouped according to the randomized treatment. If there are dose reductions during the study, key safety analyses will be grouped by the reduced dose treatment arm. P-values from statistical tests of treatment effects in safety analyses should be interpreted with caution as the analyses are intended to be descriptive and should not be considered as formal hypothesis testing. P-values and CIs, if reported, provide some evidence of the strength of the finding.

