6.6. Dose Modification

Dose adjustments for individual subjects are not planned for this study.

However, during the course of the study, the dose for a study arm may be lowered for safety reasons. The Assessment Committee may review unblinded safety data throughout the study (Section [8.4.7](#)) to assess the incidence and nature of significant AEs (including adverse events of special interest [AESIs, Section [8.2.2](#)]).

On the basis of emerging safety information, the Assessment Committee will determine whether any LY3337641 dose level(s) should be reduced in order to maintain continued subject safety. Reduction of LY3337641 dose level(s) in this study will not require a protocol amendment, but all sites will be notified in writing. For example, if subjects in a 30-mg arm report any AEs that prompt the Assessment Committee to endorse a dose reduction for all subjects in that arm, the committee may select a lower dose reassignment, based on the nature and clinical course of the

reported AE. In this example, if a 10-mg dose reassignment is selected, all active subjects in the 30-mg arm will exchange their study drug supply for new study drug in a blinded fashion and continue dosing at the reduced dose; any new subjects randomly assigned to the 30-mg dose arm will receive only the reduced dose during their study participation. Subjects in the 5-mg, 10-mg, or placebo arm will continue at their current doses but will also participate in the study drug exchange in order to maintain the study blind for all subjects; this exchange will be carried out for all subjects using the IWRS.

If the Assessment Committee determines that it is appropriate to reduce the dose below 5 mg qd, the dose and/or frequency of administration for ALL subjects on LY3337641 (whether randomly assigned to a 30-, 10-, or 5-mg arm) will be reduced. As above, all active subjects in the study (including those receiving placebo tablets) will participate in the study drug exchange in order to maintain the study blind.

If the Assessment Committee decides to reduce any study arm dose of LY3337641, a return to the original dose will not be permitted in any part of the study. However, doses may be adjusted to levels that are intermediate to the dose levels planned, as long as they are lower than doses that have been discontinued for safety reasons.

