6.1. General Statistical Considerations

Statistical analysis of this study will be the responsibility of Eli Lilly and Company or its designee.

This plan describes a priori statistical analyses for safety, efficacy, and health outcomes data that will be performed.

In general, continuous variables will be summarized including number of observations, mean, standard deviation (SD), minimum, median, and maximum values. Categorical variables will be presented as counts and percentages. Data from Part A will be summarized separately from data from Part B. No statistical hypothesis testing is planned for Part A. All tests of treatment effects in Part B will be conducted at the 2-sided α level of .05, unless otherwise stated. No adjustments for multiplicity will be performed.

Unless otherwise specified, statistical analyses to compare treatment groups will use statistical techniques with treatment group and randomization strata [ie, biologic DMARD experience (yes/no), region (Japan versus non-Japan), and baseline DAS28-hsCRP (continuous)] as factors. In addition, for analysis of continuous measures, the baseline value of the dependent variable will be included as a covariate. Fisher's exact test will be used for the analysis of categorical measures unless otherwise specified.

P-values from statistical tests of treatment effects in safety analyses should be interpreted with caution as the analyses are intended to be descriptive and should not be considered as formal hypothesis testing. P-values and confidence intervals (CIs), if reported, provide some evidence of the strength of the finding.

For the purpose of presentation, the treatment groups of Parts A and B will be assigned by randomized treatment, and the treatment groups of Follow-up period will be assigned by the last used treatment.

The analyses for the optional long-term extension is described in Section [6.5.5](#).

Additional exploratory analyses of the data will be conducted as deemed appropriate.

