6.4.2. Adverse Events

Adverse events (AEs) will be classified by SOC and PT as defined by the MedDRA®.

A TEAE is defined as an event that first occurs or worsens in severity after baseline. The MedDRA Lowest Level Term (LLT) will be used in the treatment-emergent computation. The maximum severity for each LLT during the baseline period will be used as baseline. The Dosing Period will be included as postbaseline for the analysis. Events with a missing severity during the Dosing Period will be considered treatment-emergent. Events at baseline with missing severity and reports with severity change during the Dosing Period will be considered as treatment-emergent. For events occurring on the day of first taking study medication, the case report form (CRF)-collected flag will be used to determine whether the event was pre- versus post-treatment.

	Baseline	Postbaseline	Analysis
Part A			
Dosing Period	All pre-existing conditions recorded at Visit 1 and any AEs recorded before the first dose of study drug (during the interval between Visits 1 and 2 and recorded with the time of onset before the first dose of study drug)	Dosing period (during the interval between Visits 2 and 5)	All AE analyses
Follow-up	All AEs recorded during the last visit before discontinuing study drug.	Safety follow-up period (during the interval between Visits 5 and 801)	Only for post-exposure emergent AE by SOC and preferred term.
Part B			
Dosing Period	All pre-existing conditions recorded at Visit 101 and any AEs recorded before the first dose of study drug (during the interval between Visits 101 and 102 and recorded with the time of onset before the first dose of study drug)	Dosing period (during the interval between Visits 102 and 106)	All AE analyses
Follow-up	All AEs recorded during the last visit before discontinuing study drug.	Safety follow-up period (during the interval between Visits 106 and 802)	Only for post-exposure emergent AE by SOC and preferred term.
Long-term Extension			
Dosing Period	Any AEs recorded during the interval between Visits 105 and 106 and recorded with the time of onset before the first dose of study drug for the long-term extension.	Dosing period (during the interval between Visits 106 and 114)	All AE analyses
Follow-up	All AEs recorded during the last visit before discontinuing study drug.	Safety follow-up period (during the interval between Visits 114 and 805)	Only for post-exposure-emergent AE by SOC and preferred term.

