For events that are sex specific, the denominator and computation of the percentage will only include subjects of the given sex. Otherwise, percentages will be calculated using the safety population as the denominator. Adverse events will be summarized as TEAEs.

In an overview table, the number and percentage of subjects who experienced a TEAE or serious adverse event (SAE), died due to an AE, or discontinued from study due to an AE will be summarized by treatment.

The frequency and percentages of subjects with TEAEs will be summarized by treatment using MedDRA PT nested within SOC. Events will be ordered by decreasing frequency within SOC. A common TEAEs (at least reported by 5% of subjects) summary will also be provided. As an additional table or figure, the percentages of subjects with TEAEs will be summarized by treatment using MedDRA PT (without regard to SOC). Events will be ordered by decreasing

frequency within PT. The frequency and percentages of subjects with TEAEs by maximum severity will also be summarized by treatment using MedDRA PT nested within SOC.

Fisher's exact test will be performed to compare percentages for each LY3337641 dose group and Placebo at both the SOC and PT levels.

Listings will be presented for all AEs, all SAEs, all AEs leading to death, all AEs leading to study drug temporary interruption, and all AEs leading to discontinuation from the study.

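### After a dose reduction, SAP 6.4 groups key safety analyses by the reduced-dose arm without splitting events at the switch, so read literally it reports higher-dose events under the lower dose

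*SAP*

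**What the plan says.** **How a reduction works.** Protocol 6.6 plans no individual dose adjustment, but the Assessment Committee may lower the dose of a study arm for safety reasons. In its example of a reduction from 30 mg to 10 mg, "all active subjects in the 30-mg arm will exchange their study drug supply" and carry on at the lower dose, while "any new subjects randomly assigned to the 30-mg dose arm will receive only the reduced dose during their study participation". Intermediate dose levels are also allowed.

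**The default grouping.** SAP 6.4 begins with "Safety analyses will be conducted by randomized treatment for Part A and Part B separately" and adds "Subjects will be grouped according to the randomized treatment". SAP 6.1 gives the same rule for display: "For the purpose of presentation, the treatment groups of Parts A and B will be assigned by randomized treatment". SAP 6.1.1 and Protocol 9.2.1 also group the safety population by randomized treatment. None of these makes an exception for a dose reduction.

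**The exception.** SAP 6.4 then says: "If there are dose reductions during the study, key safety analyses will be grouped by the reduced dose treatment arm". It does not define which analyses are key. It does not say whether the reduced arm is merged with an existing arm at the same dose, or whether this grouping replaces or supplements the randomized-arm tables.

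**Counting rules.** SAP 6.4.2: "A TEAE is defined as an event that first occurs or worsens in severity after baseline". For Part B the postbaseline window is the whole interval from Visit 102 to Visit 106. On denominators, apart from sex-specific events: "Otherwise, percentages will be calculated using the safety population as the denominator". SAP 6.4.1 gives each subject one duration of exposure, adjusted only for interruptions.

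**The concern.** Safety at 5, 10 and 30 mg is a primary objective of both parts. An arm's dose is lowered only for safety reasons, so the rule comes into play just when attributing events to the right dose matters most.

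Suppose a subject has a rash on Day 20 at 30 mg and the arm is exchanged to 10 mg on Day 30. The event belongs to 30 mg. A rule that groups the subject under the reduced dose, with no split at the exchange, reports it at 10 mg. Enough such events would make the lower dose look less safe and, if arms are merged, the higher dose less harmful. Rash is the one event that Protocol 8.2.2 names as an AESI, and Protocol 4.5 describes it as the commonest significant finding at high Phase 1 doses.

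**Working it through.** **1. The plan's own figure.** The arm size used below comes from SAP 5.2: 30% versus 55% ACR20, two-sided 0.05, 80% power. With pooled variance, n = [1.96·√(2·0.425·0.575) + 0.842·√(0.30·0.70 + 0.55·0.45)]² / 0.25² ≈ 60.2, which rounds up to 61 per arm (4 × 61 = 244). Power at 61 is 80.5%. The figure reproduces and is not in dispute.

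**2. Which dose does an event fall under?** After a reduction, three kinds of subject can share one randomized arm:

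- *Switched during treatment:* exposed to both doses. The subject is the unit of grouping, the TEAE window is not split and there is no new baseline at the switch. On the literal reading, all of this subject's events go to the reduced dose.
- *Stopped before the exchange:* never took the reduced dose. Protocol 7.1.2 says such subjects should also leave the study. They are counted under the reduced dose only if the whole arm is relabelled, which the SAP does not settle.
- *Randomized after the reduction:* reduced dose only, so correctly labelled.

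No rule in SAP 6.4.1, 6.4.2 or 6.4.5.2 assigns an event to the dose at onset. The follow-up grouping, by last treatment used, is also per subject.

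**3. Size if the reduced arm is merged with an existing arm.** The documents give no event rates or switch fractions, so all of these are assumptions: risk 5% at the reduced dose and in the existing arm; risk p at the higher dose; m of 61 subjects treated at the higher dose before the exchange, each given risk p; the whole arm relabelled.

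Merged rate = [m·p + (61 − m)·0.05 + 61·0.05] / 122

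| m (share of arm) | p = 10% | p = 15% | p = 20% |
|---|---|---|---|
| 15 (25%) | 5.6% (1.12×) | 6.2% (1.25×) | 6.8% (1.37×) |
| 30 (49%) | 6.2% (1.25×) | 7.5% (1.49×) | 8.7% (1.74×) |
| 46 (75%) | 6.9% (1.38×) | 8.8% (1.75×) | 10.7% (2.13×) |

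The multiples are relative to 5%. For the middle cell: (4.5 + 1.55 + 3.05)/122 = 9.1/122 = 7.5%.

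**4. Size if the reduced arm is its own row.** With m = 30 and p = 15%, the rate is (4.5 + 1.55)/61 = 6.05/61 = 9.9%. The randomized 30 mg arm holds the same 61 subjects and has the same 9.9%. No event moves between rows; only the dose attached to the row can mislead.

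**5. Dilution in counts.** Assume 61 per arm, 1 event on placebo, 1 in the randomized 10 mg arm, and in the 30 mg arm k events before a reduction to 10 mg and 1 after. P-values are from Fisher's exact test against placebo.

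| k | Randomized 30 mg arm | Merged 10 mg column |
|---|---|---|
| 3 | 4/61 = 6.6%, p = 0.36 | 5/122 = 4.1%, p = 0.67 |
| 6 | 7/61 = 11.5%, p = 0.061 | 8/122 = 6.6%, p = 0.28 |
| 9 | 10/61 = 16.4%, p = 0.008 | 11/122 = 9.0%, p = 0.064 |
| 12 | 13/61 = 21.3%, p = 0.001 | 14/122 = 11.5%, p = 0.022 |

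The randomized 10 mg arm alone is 1/61 = 1.6%.

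**The case against.** The best defence is that the sentence is undefined, not wrong. It covers only key analyses, may add to the randomized-arm tables instead of replacing them, and nowhere says that arms are merged. Much of this stands, and it rules out several stronger readings that a reader might infer:

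- *That the SAP expressly moves the events that triggered the reduction to the lower dose.* It does not say so. Subjects who stopped because of such an event move only if the whole arm is relabelled.
- *That the lower-dose rate is overstated 1.25 to 3.3 times even when the arm is shown separately.* Those multiples come from comparing the separate row with 5%. The randomized-arm table would show the same rate, so this is a labelling effect.
- *That the safety signal disappears.* SAP 6.4.2 lists all AEs, SAEs and AEs leading to interruption or discontinuation. SAP 6.4.5.2 lists rash by preferred term, grade and relatedness. The Assessment Committee reviews unblinded safety data during the study.

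It is also true that SAP 6.4 treats safety p-values as descriptive, and that the rule concerns only safety analyses.

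The defence does not remove the core problem. Under the stated rule a switched subject is classified whole, with earlier events attached. Moving only the switched subjects does not help: it carries those events across and also divides a randomized arm by who remained on drug. An analysis restricted to time after the reduction would need a baseline and an exposure definition that SAP 6.4.1 and 6.4.2 do not supply.

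**Conclusion.** The point holds as a contingent flaw in the safety summaries. If a dose is reduced, the SAP 6.4 sentence departs from the randomized grouping used elsewhere and, read literally, reports a switched subject's higher-dose events under the reduced dose. Events in subjects who stopped before the exchange are added only if the whole arm is relabelled.

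The size depends on presentation. Merging with an existing arm inflates the lower-dose rate about 1.1 to 2.1 times under the assumed risks and dilutes the higher-dose signal. Merging needs an existing arm at the reduced dose, so it does not arise at an intermediate level. A separate row holding the whole arm keeps the randomized arm's rate, and only its label misleads. Every rate and switch fraction here is an assumption. There is no effect if no dose is reduced, and individual events can still be found in the listings.

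**What to change.** Replace the sentence in SAP 6.4 with a rule to this effect:

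> After any dose reduction, safety tables by randomized arm remain the main display. TEAEs, SAEs, AEs leading to discontinuation, rash and laboratory abnormalities are also summarized by the dose being taken at onset. Events and exposure are split at each subject's study drug exchange date. The denominator at each dose is the number of subjects who took at least 1 dose at that level, and exposure-adjusted incidence is shown as well.

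This names the affected analyses and restores agreement with SAP 6.1 and 6.1.1 and Protocol 9.2.1. SAP 6.4.1 should compute exposure separately before and after the exchange date. Protocol 6.6 says that exchanges run through the IWRS, but not that the date reaches the analysis data, so the data specifications should require it.

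The cost is a wording change, plus a few tables produced only if a reduction occurs. A subject can appear in two dose rows, so those rows are not a randomized comparison; the randomized-arm tables serve that purpose. No dose or reduction rule is proposed.
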